2B. Evaluate additional measures of postsurgical recovery that are part of a comprehensive pediatric acute pain clinical trial. In addition to pain intensity and physical recovery, core outcome measures for pediatric acute pain trials include global satisfaction with treatment, emotional response to pain, adverse events (AEs), and economic factors. *Working hypothesis:* Parental and patient satisfaction, the emotional response to pain, and unexpected AEs may also influence patient recovery. *Expected outcome:* Comprehensive data on the effect of the intervention can be obtained based on consensus guidelines for pediatric acute pain clinical trials.

Outcomes Aim 1

Primary outcome: Opioid use in OMEs/kg during the first 12 hours after surgery

Secondary outcomes: 1) Opioid use in OMEs/kg at 3 additional time points: > 12 to 24 hours, > 24 to 48 hours and total during the first 48 hours after surgery 2) Pain intensity during the first 48 hours after surgery, as measured by averaging individual patient pain scores at 3 times points: within the first 12

hours, > 12 to 24 hours, and > 24 to 48 hours after surgery using developmentally appropriate assessment tools.

Outcomes Aim 2 (Exploratory)

Aim 2A Outcomes

Length of hospital stay (hours) defined by time of PCICU admission to time of discharge. Physical recovery outcomes from time (h) of PCICU admission to: 1) mobilization, defined as first time out of bed; 2) enteral intake, defined as $\geq 50\%$ of meal consumed by mouth; 3) removal of indwelling chest tube and arterial line.

Aim 2B Outcomes

1) Global patient and parental satisfaction with pain management and inpatient care; 2) emotional response in patients ≥ 12 years of age 3) direct hospitalization costs 4) pain intensity 3 months after surgery; and 5) adverse events (AEs).

Background & Significance

Pediatric cardiac surgery patients are highly sensitive to hemodynamic and metabolic changes. Lack of compensatory mechanisms for pain-related tachycardia, hypertension, and tachypnea may lead to devastating post-surgical outcomes. Therefore, adequate pain control in this population is essential to ensure timely convalescence, particularly in the first 12 hours after surgery, when pain has been reported to be the highest.

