We postulate that the proposed combination of regional anesthesia techniques will improve pain control, decrease opioid use, enhance recovery, increase satisfaction, and decrease costs in children undergoing septal defect repairs at our institution. If effective, this intervention may be reproduced at other centers and applied broadly for use for patients eligible for early extubation after pediatric cardiac surgery. Within the context of expanding ERAS protocols, the **impact** of this research will provide strong preliminary evidence to incorporate these pilot study results into enhanced recovery programs for pediatric cardiac surgery patients around the country.

Design & Procedures

We will conduct a single center, prospective, randomized, double-blind clinical trial with an active comparator arm. Subjects will be randomized 1:1 to either fascial plane blocks or surgeon-administered local anesthesia wound infiltration using randomization tables generated by The Biostatistics Group within the Department of Anesthesiology. Each subject will be assigned the next number.

Perioperative Care:

Anesthesia and surgical care will not be altered for this study except for randomization to the study intervention group. Oral or IV midazolam for anxiolysis may be given at standard dosing. Inhaled sevoflurane or intravenous agents will be administered at the anesthesiologist's discretion to induce general anesthesia.

Intraoperative Opioid Management: Since 2018, we have used a standardized weight-based intraoperative methadone protocol for all pediatric cardiac surgeries at our institution. This study will follow this well-established protocol. All patients will receive a dose of 0.1 mg/kg of methadone administered at 3 time points during the procedure: on induction of anesthesia, on incision, and on initiation of cardiopulmonary bypass (given to the perfusionist to administer). Per protocol, additional doses of 0.05-0.1 mg/kg methadone may be given at the discretion of the anesthesiologist following separation from bypass, up to 0.4 mg/kg total during the case. No patients will receive additional supplemental opioids intraoperatively.

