Sample Size Analysis: We have calculated that a sample size of 60 total patients provides > 80% power to detect an effect size (Cohen's d) of 0.9 with a significance level of $\alpha = 0.05$. For our primary outcome, opioid use during the first 12 hours postoperatively, a larger effect size of approximately 1.1 has been documented in our previous retrospective observational study, but a smaller effect size was chosen to allow for potential residual confounding. Based this primarily data, this effect size would correspond to a reduction in OME of approximately 0.32 mg/kg. The same retrospective study reported an estimated difference in LOS of 22 hrs with a pooled standard deviation of 24.4 hrs, corresponding to a Cohen's d of 0.9. For the secondary outcome of pain intensity, a Cohen's d effect size of 1.1 was demonstrated in our preliminary work, corresponding to a difference in pain scores of 1.7 points. In summary, our planned sample size of 60 patients provides 80% power to detect an effect with a Cohen's d effect size of 0.9, which is consistent with effect sizes seen in our preliminary data for opioid utilization, length of stay, and pain intensity.

Planned Data Analysis: Descriptive statistics for each treatment group will be computed for patient demographic and characteristic variables. Since our randomization scheme will have balanced the age effect between treatment groups, we anticipate that the demographic and patient characteristic variables will be balanced across groups. For the primary and secondary continuous outcome measures including opioid use, pain scores, time to mobilization, time to enteral intake, time to removal of chest tube and arterial line, and length of stay, we will conduct two-sample *t*-tests to determine the difference in means (e.g., OME difference) between treatment groups. For continuous exploratory outcomes, including patient and parent satisfaction, hospitalization costs, pain 3 months after surgery, and emotional response, groups will be compared using Wilcoxon Rank-Sum tests. For the categorical exploratory outcome of adverse events, chi-square or Fisher's exact tests will be applied as appropriate. Results with $p < 0.05$ will be considered statistically significant. Point estimates and 95% confidence intervals (CIs) for the difference in means will be reported for all continuous outcomes, and odds ratios and associated CIs will be reported for categorical outcomes.

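### Age balance is credited to a randomization scheme that names no age strata, and opioid use and pain scores get unadjusted t-tests: valid, but possibly less precise than they could be

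*Combined protocol and SAP*

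**What the plan says.** Under Data Analysis & Statistical Considerations, the Planned Data Analysis paragraph starts from the premise "Since our randomization scheme will have balanced the age effect between treatment groups" and draws from it the expectation "we anticipate that the demographic and patient characteristic variables will be balanced across groups". Baseline variables have a descriptive role only: "Descriptive statistics for each treatment group will be computed for patient demographic and characteristic variables". Opioid use, pain scores, recovery times and length of stay are compared by two-sample t-tests "to determine the difference in means (e.g., OME difference) between treatment groups", with 95% confidence intervals. No covariate, adjusted model or sensitivity analysis is mentioned.

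The scheme is described only under Design & Procedures: "Subjects will be randomized 1:1 to either fascial plane blocks or surgeon-administered local anesthesia wound infiltration using randomization tables", and "Each subject will be assigned the next number". No section mentions strata, blocks or minimisation.

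The outcomes concerned are "Primary outcome: Opioid use in OMEs/kg during the first 12 hours after surgery", the later opioid windows, and pain intensity scored "using developmentally appropriate assessment tools". Selection of Subjects admits all children under 18 and sets no minimum age.

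**The concern.** The analysis paragraph treats age balance as something the design delivers, but the design section does not show how. The sentence can be read in two ways:

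- The tables are stratified by age. The protocol then leaves out its strata, and the analysis ignores them.
- The tables are not stratified. Age is then balanced on average, but not necessarily in the 60 children enrolled.

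The sponsor knows which applies; the reader cannot tell.

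The plan itself singles out age, and it contains routes by which age could affect the outcomes. Pain tools vary with development. Under Postoperative Care, opioids are given on pain-scale assessments, and NSAIDs are restricted to children above 6 months. The documents give no size for any such effect. Reporting opioid use per kg may already remove part of it.

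What is at stake is the width of the confidence intervals for opioid use and pain. If age is prognostic, an unadjusted comparison leaves its variance in the error term.

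**Working it through.** **Inputs from the documents.** N = 60 at 1:1, so 30 per arm; d = 0.9; alpha 0.05 (taken as two-sided); an OME difference of 0.32 mg/kg; a pain difference of 1.7 points at d = 1.1 (Sample Size Analysis).

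**Assumptions, because the documents give no figure.** R2, the share of within-arm outcome variance explained by age, is 0.04 to 0.4. Age distribution and shape of the age effect are also assumed.

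**1. The plan's own figure.** Noncentrality = 0.9 × sqrt(30/2) = 3.486; with 58 df the critical t is 2.002; power = 92.9%. The stated figure of more than 80% is reproduced with room to spare.

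**2. What unstratified 1:1 allocation guarantees about age.** The SE of the standardized age difference is sqrt(2/30) = 0.258. P(difference > 0.3 SD) = P(|Z| > 0.3/0.258) = 24.5%. For 0.5 SD it is about 5%. The cut-offs are illustrative, and the same figures hold for any baseline variable.

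**3. Validity of the unadjusted t-test (simulated).**
- Unstratified: type I error 4.8% to 5.2%.
- Stratified at the median age, effect linear in log age: 4.6%, 4.1%, 3.6% and 2.2% at R2 = 0.04, 0.1, 0.2 and 0.4.
- Three strata of 20, normally distributed covariate: 4.3%, 2.5% and 1.3% at R2 = 0.1, 0.3 and 0.5.
- Median split with log age and stratum in the model: 4.8% to 5.2%.

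**4. Precision.** If the covariate has the right shape, the SE is multiplied by about sqrt(1 - R2): 0.949 at R2 = 0.1 and 0.775 at R2 = 0.4. If the shape is wrong, the gain shrinks. Simulated SE change against the unadjusted test, with skewed (truncated log-normal, median 2.3 years) ages, at R2 = 0.04 / 0.2 / 0.4:

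| True age effect | Adjusting for log age | Adjusting for linear age |
|---|---|---|
| Linear in log age | -1.2 / -9.8 / -21.9% | not run |
| Linear in age | -0.6 / -6.9 / -15.4% | not run |
| Youngest fifth only | -0.2 / -4.7 / -10.7% | +0.5 / -1.0 / -2.9% |
| Oldest fifth only | -0.0 / -3.9 / -8.9% | -0.5 / -6.6 / -14.5% |
| 12 years and above only | +0.6 / -0.8 / -2.5% | -0.0 / -4.1 / -9.1% |
| Both extremes | +0.9 / +0.8 / +0.7% | not run |

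With no age effect, the SE goes from 0.2570 to 0.2593 (+0.9%) and power from 93.1% to 92.7%. With a median-split stratum also in the model, power goes from 92.8% to 92.2%.

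**5. In outcome units.** 95% CI half-width = 2.002 × 0.258 × SD, then multiplied by 1.009 (worst case) or 0.78 (best case):
- OME, SD = 0.32/0.9 = 0.356: 0.184 mg/kg, becoming 0.185 to 0.143.
- OME, SD = 0.32/1.1 = 0.291: 0.150 mg/kg, becoming 0.152 to 0.117. The text does not make clear which d the 0.32 belongs to.
- Pain, SD = 1.7/1.1 = 1.545: 0.798 points, becoming 0.805 to 0.622.

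**The case against.** The strongest defence is that randomization needs no help here. Chance imbalance in age is already covered by the 5% error rate, power is ample, the trial calls itself a pilot, and nothing in the documents shows that age predicts opioid use per kg. All of this stands.

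It also disposes of three stronger readings that a reader might infer:

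- **That an age imbalance would bias or invalidate the t-tests.** Step 3 shows it would not.
- **That the plan has no answer if the arms turn out to differ in age.** It has one: the t-test with its interval is fixed in advance and does not depend on observed balance.
- **That log age is the safer covariate because effects should be steepest in the youngest.** The documents give no direction or shape. In the table, log age does better for an effect in the youngest fifth, linear age does better for effects in older children, and log age gains nothing if both extremes are affected.

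The defence does not show how the scheme balances age, and it does not remove the asymmetry in step 4. Adjustment costs at most about 0.9% in SE under these assumptions and may save up to 22%. If the tables are age-stratified and age is prognostic, the planned test is needlessly conservative.

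**Conclusion.** This is a minor point that holds. The age-balance statement has no support in the description of the scheme, and the opioid and pain comparisons forgo an adjustment that is nearly free. Type I error is controlled, and power at the planned effect is about 93%, so the planned inference does not depend on this change.

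The size of the precision loss cannot be computed from the documents. The range of +0.9% to -22% rests wholly on assumed R2 values, age distributions and effect shapes. The favourable end needs R2 = 0.4 with a correctly shaped covariate, and the low end is plausible for an outcome already scaled by weight. The stratified figures likewise assume strata that no section describes. A reader might conclude that the tables are unstratified; the text does not establish that either.

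**What to change.** 1. In Planned Data Analysis, replace the age-balance statement with the scheme actually used: simple, blocked or stratified, and the strata if any.
2. Before unblinded analysis, prespecify for opioid use (primary) and pain scores a linear regression on treatment and age, plus any stratification factor actually used. The statistician should choose one fixed functional form for age without sight of outcomes by arm. Neither log nor linear is shown to be better.
3. Report the adjusted mean difference with its 95% CI, and keep the unadjusted t-test as sensitivity analysis.
4. Recovery times and length of stay are listed as exploratory under Outcomes Aim 2, so the same model is optional there.

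The cost is SAP wording, one of 58 residual degrees of freedom for age (plus one fewer than the number of strata, if strata are included), and about 0.5 point of power at d = 0.9 if age is not prognostic. Age is already needed for eligibility and for assigning the surveys. Enrollment and the randomization tables do not change.

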Official Title: Pain Control with Regional Anesthesia following Pediatric Cardiac Surgery: A Randomized Double-Blinded Pilot Study

Protocol#: Pro00111671

NCT#: NCT05688670

Document Date: 10/24/2024

Standard Research Summary

Purpose of the Study

Overall Aim: The overall objective of this study is to characterize the analgesic effect of a novel combination of bilateral Pecto-Intercostal Fascial Blocks (**PIFBs**) and a unilateral Rectus Sheath Block (**RSB**) in pediatric patients undergoing primary septal defect repairs. The *central hypothesis* is that together, bilateral PIFBs and a unilateral RSB provide superior pain control, reduce postoperative opioid use, and improve postoperative recovery compared to surgeon-delivered local anesthetic wound infiltration.

Aim 1. Assess postoperative pain intensity and opioid use in the first 48 hours after surgery. Patients will receive a standardized protocol-driven postoperative pain regimen in the Pediatric Cardiac Intensive Care Unit (PCICU). *Working hypothesis:* PIFB/RSB-treated patients have statistically lower postoperative pain intensity and opioid use in the first 48 hours after surgery vs patients who receive local anesthetic infiltration. *Expected outcome:* The analgesic effect of the proposed intervention will be greater than that of the control group.

Aim 2. Assess outcomes associated with improved postoperative recovery as defined by consensus guidelines for pediatric acute pain clinical trials (PedIMMPACT).

2A: Evaluate outcome measures associated with postoperative physical recovery. Early extubation, multimodal pain regimens, and prevention of postoperative nausea and vomiting are key metrics of ERAS protocols in children undergoing cardiac surgery. *Working hypothesis:* Within the framework of a standardized ERAS protocol, PIFB/RSB-treated patients have earlier functional recovery compared to the control group. *Expected outcome:* PIFB/RSB-treated patients will have a decreased time to mobilization and enteral intake, earlier removal of lines and drains, and shorter hospital length of stay.

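### The p < 0.05 significance label covers about 18 non-primary tests, about 12 of them on outcomes the plan calls exploratory, with no hierarchy or multiplicity control

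*Combined protocol and SAP*

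**What the plan says.** The outcome lists under Purpose of the Study name one primary outcome, opioid use in the first 12 hours. They add six Aim 1 secondary comparisons: three further opioid windows and three pain windows. Everything under Aim 2 sits below a heading marked "Outcomes Aim 2 (Exploratory".

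Planned Data Analysis then assigns the tests. For a group it introduces as primary and secondary continuous measures, "we will conduct two-sample *t*-tests to determine the difference in means". That group includes the recovery times and length of stay, which the outcome list places in exploratory Aim 2A. Satisfaction, cost, 3-month pain and emotional response get Wilcoxon tests, and adverse events get chi-square or Fisher tests; here the section does use the word exploratory. The next sentence states that any result with p < 0.05 "will be considered statistically significant". It is not limited to the primary outcome.

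The document has no testing order, no adjustment, and no statement that any p-values are nominal. It does promise estimates with 95% CIs for all continuous outcomes, and odds ratios with CIs for categorical ones.

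**The concern.** A 5% threshold limits the error rate of one test. Applied to every result, it limits nothing across the set, and it gives an exploratory finding the same words as the primary one. That conflicts with the plan's own separation of primary, secondary and exploratory outcomes. The separation is further blurred because Planned Data Analysis groups the Aim 2A outcomes with the primary and secondary ones, and because length of stay is used in support of the sample size.

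At stake is how the report will read. Under Background & Significance the sponsor expects the results to serve as preliminary evidence for enhanced recovery programs nationally. Under the present sentence, a chance difference in length of stay, cost or satisfaction could be reported there as statistically significant without departing from the plan.

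**Working it through.** **Plan's own figure.** Sample Size Analysis states that "a sample size of 60 total patients provides > 80% power to detect an effect size (Cohen's d) of 0.9". With 1:1 allocation (30 per arm), a two-sided t-test at 0.05 and d = 0.9, the noncentral t gives power of 92.9%, so the statement is correct as a bound. The plan does not state sidedness; two-sided is assumed throughout. The plan gives no family-wise error rate and no number of tests to reproduce.

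**Count of tests**, from the outcome lists, the Surveys list and Planned Data Analysis:

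| Outcome group | Label in outcome list | Tests |
|---|---|---|
| Opioid use, 0-12 h | Primary | 1 |
| Opioid use, >12-24 h, >24-48 h, total 48 h | Secondary | 3 |
| Pain intensity, three windows | Secondary | 3 |
| Mobilization, enteral intake, chest tube, arterial line, length of stay | Exploratory (2A) | 5 |
| Three satisfaction instruments, cost, 3-month pain, emotional response | Exploratory (2B) | 6 |
| Adverse events | Exploratory (2B) | 1 or more |

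Total 1 + 3 + 3 + 5 + 6 + 1 = 19, of which 18 are not primary. Treating satisfaction as two outcomes gives 18 in all; testing adverse events by type gives more.

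**Expected false positives under no effect.** 18 × 0.05 = 0.9 in either direction, whatever the correlation. Half of these, 0.45, would favour the block.

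**Chance of at least one among the 18.** If independent:
- either direction: 1 − 0.95^18 = 0.603;
- favouring the block: 1 − 0.975^18 = 0.366.

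The outcomes are related, and total 48-hour opioid use is the sum of its windows, so independence is an upper reference. For equally correlated normal test statistics, scored so that benefit points the same way, numerical integration gives:

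| Assumed pairwise correlation | Either direction | Favouring the block |
|---|---|---|
| 0 | 60% | 37% |
| 0.3 | 51% | 26% |
| 0.5 | 40% | 20% |
| 0.7 | 28% | 14% |

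The either-direction figure falls below 50% at a correlation of about 0.32.

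**Six secondaries alone.** 1 − 0.95^6 = 0.265 if independent, 24% at correlation 0.3 and 21% at 0.5. Favouring the block: 14%, 12% and 10%.

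**Cross-check.** A patient-level null simulation of all 19 tests used 30 per arm and 6,000 runs per scenario, with total opioid use built as the sum of its windows. It assumed 25% of patients aged 12 or over and a 20% adverse-event rate. The chance of any false positive among the 18 non-primary tests ran from 57% (no correlation) to 33% (0.8 within and 0.6 between outcome groups). Across all 19 tests the mean number of false positives was about 0.9 in every scenario. The primary test alone stayed at about 5%.

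**Alternatives compared.** Bonferroni over the seven Aim 1 tests would cut primary power at d = 0.9 from 92.9% to 75%; over all 19 tests, to 63%. Testing the primary first at 0.05, then applying Holm to the six secondaries (smallest p-value against 0.05/6 = 0.0083), holds the seven-test family at 5% and leaves primary power at 92.9%.

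**The case against.** The best defence is that this is a pilot with one pre-specified primary outcome, that Aim 2 is openly labelled exploratory, and that unadjusted tests of exploratory outcomes are conventional in such a trial. Estimates and intervals are already promised, so little is missing. This stands as far as it goes: no adjustment of the exploratory tests is needed. It does not answer the sentence itself, which follows directly on the exploratory tests and attaches the word significant to them.

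Two further objections also stand. First, a two-sided error can go against the block; only about half of the false positives would support it, so the favouring-the-block figures are the relevant ones for overclaiming. Second, limiting significance to the primary outcome alone would sit badly with Aim 1, whose working hypothesis predicts statistically lower pain and opioid use over 48 hours. The fix therefore has to allow a route for the Aim 1 secondaries.

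A reader might also infer that success on any one part of the central hypothesis would count as support for the block. The Overall Aim does not say so. It expects the blocks to "provide superior pain control, reduce postoperative opioid use, and improve postoperative recovery", with the parts joined by *and*, and no section defines success as any one of them.

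**Conclusion.** The point holds as one about labelling. The plan lets about 18 non-primary results be called statistically significant without any control of error across them, including about 12 that it labels exploratory. Under no effect, the chance of at least one such result is 60% at most for 18 tests under the correlations considered, about 40% at correlation 0.5 and 28% at 0.7. In the block's favour it is about 37% down to 14%.

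These figures rest on the count of 18, two-sided tests at their nominal size, and assumed correlations that the documents do not give.

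Two stronger readings are not supported. A false significant finding cannot be called likely: that needs weak correlation, which the documents do not establish, and for findings favouring the block the chance is below one half in every case shown. Nor is the primary analysis compromised: its 5% error rate and its power are intact. The change should be made, but it is a change of wording.

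**What to change.** Replace the significance sentence in Planned Data Analysis with text to this effect:

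*Statistical significance at two-sided 0.05 will be claimed for the primary outcome (opioid use, 0-12 h). Only if it is significant, the six Aim 1 secondary outcomes will be tested with the Holm procedure at an overall two-sided 0.05. All Aim 2 outcomes will be reported as estimates with 95% confidence intervals; any p-values for them are nominal and will not be called statistically significant.*

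If the sponsor prefers, the six secondaries can be reported as nominal too.

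In the same section, move the Aim 2A recovery times and length of stay out of the primary and secondary group, so that they carry the exploratory label used in the outcome list.

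The cost is a few sentences of text. The primary test, its power and the sample size of 60 do not change, and the planned estimates and intervals stay. The small downside is that fewer results can be called significant.

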Patients will be screened and properly identified by the principal investigator or member of the clinical research team via an IRB-approved review of the surgery schedule. An IRB-approved phone call may be conducted to introduce the study or patients may be approached on the day of surgery allowing sufficient time for explanation, questions and answers. If interested, parents or legal guardians may provide consent for the study in advance via an IRB-approved electronic Informed Consent Form or a paper consent may be obtained on the day of surgery.

Goal recruitment is 60 subjects to complete the study. Subjects will be compensated \$20 gift card (mailed) for the time and effort to complete the surveys and phone call on day 30 after surgery.

Subject's Capacity to Give Legally Effective Consent

Parental/guardian permission will be sought first for study enrollment. In the case that subjects are 12 years and older, patient assent for enrollment in the study will then be obtained. If <12 years of age, only parental/legal guardian consent will be obtained for patient participation.

Study Interventions

The study related treatment is not investigational. Ropivacaine is a standard of care medication being used at standard doses.

Risk/Benefit Assessment

Recruitment and Informed Consent: The study will be conducted under appropriate Duke University IRB protocol and consent form approvals. The study will be conducted under the supervision of the PI, who is a Board-Certified pediatric anesthesiologist ([name]) with experience conducting clinical trials in children. Potential subjects will be identified through IRB-approved review of the surgical schedule prior to their surgery, at which time they will be contacted and asked if they are interested in participating. An IRB-approved phone screen will be conducted. Subjects that wish to participate may sign paper consent on the day of surgery when allowing sufficient time for explanations, questions and answers. If interested and willing, subjects may also be fully consented using IRB approved eICF. Informed consent must be given and signed by parents and/or legal guardian. Children greater than or equal to 12 years of age must provide verbal assent to be in the study.

Risks:

The safe and effective use of local anesthetics depends on proper dosage, correct technique, adequate precautions and readiness for emergencies.

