The Duke Children's Pediatric and Congenital Heart Center is the 10th largest pediatric and congenital heart program in the country. In order to recruit 60 patients during the 1-year grant period, we would need 60% enrollment. We believe this is feasible for our study because 1) the intervention is low-risk, 2) the surveys are brief; there are no painful procedures (blood draws); and follow up requirements are minimal; 3) the surgeons and PCICU team strongly support the study; 4) the research environment is robust, well established, and dedicated to clinical trial work; and 5) the study team is led by a well-supported PI and an experienced mentor who have successfully worked together on a prior pediatric pain RCT.

Data & Safety Monitoring

Data are collected and stored via REDCap. The REDCap servers are securely housed in an on-site limited access data center managed by the Division of Biostatistics. All web-based information transmission is encrypted, and the data is stored on a private, firewall protected network. No identifiable data will be stored on personal computers or laptops. Data will be exported from REDCap for statistical analysis with patient identifying information removed. The consent form, medical information, and case report forms will be stored under lock and key (office, file cabinet) and only the PI, physician investigators, and research team will have access.

As noted above, all patients will receive continuous invasive monitoring postoperatively in the PCICU as per standard of care. Local anesthetic doses are standardized and chosen to prevent local anesthetic systemic toxicity (LAST). We have completed over 100 of these blocks in this population since June 2021. There has been no concerns of LAST and this regional block was specifically chosen to avoid a fascial plane with large blood vessels; however, in a suspected case of LAST, Intralipid 20% would be given as per standard protocol with weight based dosing. Signs and symptoms of LAST typically occur in the first 1-5 minutes after delivery of local anesthetic; therefore this rare complication would likely occur while the patient is still in the operating room.

Any potential study related AE will be immediately reported to the PI, study team, CRU practice managers, and IRB.

Unblinding Procedures:

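### Adverse events are to be compared by odds ratio alone with about 30 children per arm; for event types with a true risk below about 4%, the ratio will more often than not be zero, infinite or undefined.

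*Combined protocol and SAP*

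**What the plan says.** The Planned Data Analysis paragraph (Data Analysis & Statistical Considerations) sets out the safety comparison in two steps. "For the categorical exploratory outcome of adverse events", a chi-square or Fisher's exact test is chosen as appropriate. On estimation, "odds ratios and associated CIs will be reported for categorical outcomes". Continuous outcomes are promised a difference in means with a 95% interval, which is an absolute measure. Adverse events get no absolute measure.

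On size, Subject Recruitment and Compensation states: "Goal recruitment is 60 subjects to complete the study". Design & Procedures states: "Subjects will be randomized 1:1 to either fascial plane blocks" or to surgeon infiltration. That is about 30 per arm.

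The documents give no adverse event rates, no list of event types to be compared, no rule for empty cells and no named method for the odds ratio interval. The Risks section lists side effects of ropivacaine without frequencies. Data & Safety Monitoring describes local anesthetic systemic toxicity (LAST) as rare and reports no concerns about it so far: "We have completed over 100 of these blocks in this population since June 2021".

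**The concern.** An odds ratio needs events in both arms to be finite and non-zero. Among 30 children, an uncommon event may well not occur at all. If one arm has none, the estimate is 0 or infinite; if neither arm has any, it is 0/0. Fisher's test remains valid with sparse counts, but a p-value does not say how large a difference the data leave open.

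What is at stake is how safety results from a small trial are read. A non-significant test with no finite estimate beside it can be taken to mean that the arms are alike, when the data exclude very little. If no rule is set in advance, the handling of empty cells (a continuity correction, an exact method or omission of the row) would be chosen after the results are known, and these choices give different numbers.

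**Working it through.** **The plan's own figure.** No figure is stated for adverse events. The only calculation based on 60 children is for the primary outcome: "a sample size of 60 total patients provides > 80% power to detect an effect size" of 0.9 at alpha 0.05. For a two-sample t-test with 30 per arm (two-sided assumed, since sidedness is not stated), the noncentral t distribution gives 92.9%, which agrees with the claim. It confirms the 30 per arm used below and has no other bearing here.

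**Inputs.** n = 30 per arm (60 completers, 1:1). True risk p per child, assumed equal in both arms; p is not in the documents, so a range is shown.

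**Chance of an empty arm.** Let q = (1 − p)^30 be the chance that one arm has no events.

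- At least one arm empty: 1 − (1 − q)²
- Both arms empty: q²
- One arm empty, given at least one event overall: 2q(1 − q)/(1 − q²) = 2q/(1 + q)

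| p | q | At least one arm empty | Both empty | One empty, given at least one event |
|---|---|---|---|---|
| 1% | 0.740 | 93% | 55% | 85% |
| 2% | 0.545 | 79% | 30% | 71% |
| 3% | 0.401 | 64% | 16% | 57% |
| 4% | 0.294 | 50% | 9% | 45% |
| 5% | 0.215 | 38% | 5% | 35% |
| 10% | 0.042 | 8% | 0.2% | 8% |

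**Where the balance tips.** Setting 1 − (1 − q)² = 0.5 gives q = 1 − √0.5 = 0.293, so p = 1 − 0.293^(1/30) = 4.0%. Among events that occur at all, 2q/(1 + q) = 0.5 gives q = 1/3 and p = 3.6%.

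**Unequal risks.** At least one arm is empty with probability 1 − (1 − q₁)(1 − q₂): 64% for 5% vs 2%, 56% for 10% vs 2%, and 25% for 10% vs 5%.

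**What each measure gives in sparse tables (block vs infiltration).**

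- 0/30 vs 0/30: odds ratio undefined, exact interval 0 to infinity. The Wilson upper limit for 0/30 is 1.96²/(30 + 1.96²) = 11.4%, so the Newcombe interval for the risk difference is −11.4 to +11.4 points.
- 2/30 vs 0/30: odds ratio infinite, conditional exact 95% interval 0.19 to infinity. The risk difference is +6.7 points, Newcombe −5.7 to +21.3.
- 5/30 vs 0/30: odds ratio infinite. Fisher's two-sided p is the chance that all five events fall in one arm, 2·C(30,5)/C(60,5) = 0.052, which is not significant at the plan's 0.05 level although the observed difference is 16.7 points.
- One arm with 0/30: exact one-sided 95% upper bound 1 − 0.05^(1/30) = 9.5%.

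**LAST as an illustration.** If the site's experience is read as 0 cases in 100, the one-sided 95% upper bound is 1 − 0.05^(1/100) = 3.0%, a risk at which an arm is still empty 64% of the time. It is not clear whether the 100 counts patients or injections. At three sites per patient it would be about 33 patients, with a bound of about 9%. This is supporting evidence only.

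**The case against.** The strongest reply is that the extent of the problem is unknown. No event rates are given, and the plan speaks of adverse events as one outcome, which can be read as a single comparison of any event. Such a comparison could well have cases in both arms and a finite odds ratio. This stands, and it is why the point is limited to event types below about 4%.

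Second, the unconditional percentages count events that never occur, for which an odds ratio would rarely be tabulated. This also stands, but conditioning on at least one event moves the threshold only from 4.0% to 3.6%.

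Third, a reader might infer that the trial would have no usable interval for safety. The documents do not support that. When only one arm is empty, an exact method gives a finite bound on one side, and events seen in both arms get an ordinary interval. Only the case of two empty arms is uninformative. The plan names Fisher's test but no interval method, so the exact bound is available without being specified.

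Fourth, a reader might add that odds ratios exaggerate differences for common events. That is so only if they are misread as risk ratios, and the plan calls them odds ratios. The documents give no frequency that marks any event as common. It is a matter of preference and no part of this point.

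Fifth, LAST is handled through monitoring, treatment and immediate reporting, not by comparing arms, and no effect measure could compare so rare an event with 30 per arm. This is correct; LAST serves only as an illustration.

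Last, a risk difference does not cure imprecision, which comes from the sample size. This is true. What it does is show the imprecision in a finite interval.

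**Conclusion.** The point holds as a modest reporting gap. For event types with a true risk below about 4% per arm, the one effect measure that the plan names will more often than not be 0, infinite or undefined, and the documents give no rule for that case. At 5% an empty arm is no longer the usual result, and at 10% it is unlikely.

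This rests on two assumptions: 30 children analysed per arm and, for the threshold, equal true risk in both. The number of event types that fall below 4% cannot be determined from the documents. Adverse events are exploratory in a self-described pilot, so the primary outcome, the power calculation and the main efficacy conclusions are untouched.

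**What to change.** Amend the estimation sentence in Planned Data Analysis so that, for any adverse event and for each event type, the report gives:

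- the number of children with the event and the number analysed, per arm;
- the risk difference (block minus infiltration) with a Newcombe 95% confidence interval;
- for any arm with no events, the exact one-sided 95% upper bound (9.5% for 0/30);
- the odds ratio with its interval only where all four cells are non-zero.

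Fisher's exact test can stay as a descriptive p-value. The change should be made before unblinding, so that the handling of empty cells is not chosen with the results in view.

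The cost is about one sentence in the plan and slightly longer tables; no new data are needed. Intervals will be wide, which correctly shows how little 30 per arm can exclude. A Newcombe interval and Fisher's test can also disagree near the margin. For 5/30 vs 0/30, the Wilson limits are 7.3% to 33.6% and 0% to 11.4%. The Newcombe interval is therefore 16.7 − √(9.3² + 11.4²) = 2.0 to 33.6 points, which excludes zero, while Fisher's p is 0.052. The plan should say that the interval is the main summary.
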